## > SYNOPSIS OF THE CLINICAL INVESTIGATION

---

### Aim and Objective

The aim of the investigation is to investigate the performance of a baseplate [REDACTED]  
[REDACTED]

The primary objective is to investigate whether a new baseplate [REDACTED]  
[REDACTED]

The secondary objective is to investigate the safety of a new baseplate [REDACTED]

### Primary endpoint and explorative endpoint(s)

**Primary endpoint:** Trans epidermal water loss (inner circle around stoma).

### Pass/fail criteria

No formal success criteria are applied in this explorative investigation. The investigation will provide valuable insight into how the peristomal skin reacts [REDACTED].

### Design of the investigation

This investigation is a controlled, comparative, multicentre investigation, that consist of two test periods. During Test Period 1 the subjects will be asked to use SenSura® Mio (Comparator) for baseline data for 14 (-2/+15) days. Hereafter they will be asked to use the test product for 28 (-4/+12) days during Test Period 2.

Before the test periods the subjects are invited for an inclusion visit (V0). Subjects sign all consent forms at this visit before continuing the investigation. Hereafter, the subjects will complete five test visits (V1, V2, V4, V5 and V6) and one safety visit at site (V3). After termination, a follow-up visit may be conducted at the subject's home.

### Population

The population in this investigation includes 25 subjects with an ileostomy or a colostomy with liquid output that comply with the following in- and exclusion criteria:

Inclusion criteria To be included the subjects must:	Exclusion criteria The subjects are not allowed to participate in case they:
Have given written informed consent	Are currently receiving or have within the past two months received radio-and/or chemotherapy (low doses chemotherapy are allowed for other indications than cancer, e.g. below 15 mg methotrexate for rheumatoid arthritis)

Have an ileostomy or a colostomy with liquid* output (as their usual output) * Bristol Scale: 6-7	Are currently receiving or have within the past month received topical steroid treatment in the peristomal skin area (e.g. lotion or spray) or systemic treatment* (e.g. injection or tablets). *Investigator will decide on case basis whether the treatment is accepted under the protocol
Be at least 18 years of age and have full legal capacity	Get a positive result of a pregnancy test for women of childbearing age/fertile (**clarified in section 6.3.2)
Have had their stoma for at least three months	Are breast feeding
Be able to use products with max cut size 45 mm	Are participating in other interventional clinical investigations or have previously participated in this investigation Exception: Participation in other Coloplast in-house clinical investigations is accepted under the circumstances that the subject has paused the activities in the investigation and are otherwise complying with the inclusion and exclusion criteria of this (CP300) protocol.
Have self-reported problems with leakage** (three times within 14 days) **Leakage: Leakage is defined as output from the stoma on the backside of the baseplate (underneath the baseplate) [REDACTED]	Have known hypersensitivity towards any of the products used in the investigation
Use a flat SenSura® Mio or a flat SenSura® with standard adhesive as their current product Standard adhesive: Not extended wear adhesive	
Minimum change of baseplate at least once every 3 rd day	
Are willing and suitable (determined by investigator/study nurse) to use the test product and comparator without using a paste/mouldable ring during the investigation	
Are willing and suitable (determined by investigator/study nurse) to use a 1-piece product during the investigation	

### Test products

The test product is a non-CE marked stoma product with flat custom cut adhesive, with open maxi bags and with the intended use of collecting output from a stoma. The product is based on the SenSura® Mio 1-piece stoma product (already CE-marked and launched), [REDACTED]

The comparator product is the SenSura® Mio 1-piece stoma product.

### 1.2. Investigators

The Coordinating Clinical Manager is responsible for maintaining an updated Site Personnel Contact Details list of all Principal Investigators, investigation sites and institutions. Details of all Principal Investigators, investigators, including a CV, are maintained in the Sponsor File.

Qualified site personnel can perform investigation related tasks as investigator representatives. This delegation will be documented in the “Site Personal Signature and Delegation List” for each site. All investigators and investigator representatives will receive oral and written training in all investigation related tasks before they can begin any investigation related tasks. The training will be documented in the Clinical Investigation Training Log at each site.

### **1.3. Other**

CROs may be used to help conduct the investigation as Sponsor representatives in one or more countries. The CROs, their role and responsibilities will be listed in the Site Personnel Contact Details list.

## 2. Identification and description of the investigational device

[figure not shown]
The test product is a non-CE marked stoma product with flat custom cut adhesive, with open maxi bags and with the intended use of collecting output from a stoma. The product is based on the SenSura® Mio 1-piece stoma product (already CE-marked and [REDACTED])

### 2.1. Manufacture

Coloplast A/S, [name], manufactures the investigational device.

### 2.2. Description of investigational device

The test product (1-piece) is based on the SenSura® Mio 1-piece product [REDACTED]

[figure not shown]

The CP300 1-piece test product consists of an adhesive baseplate (125×105 mm) [REDACTED] The baseplate consists of a top film carrying [REDACTED] facing the user's skin. The bag is equipped with an outlet plate and a carbon filter. The bag is welded to the baseplate [1].

### 2.3. Identification, traceability and labelling of device

The products will be packed in retail boxes with ten 1-piece products in each box. Labelling of the test products (1-piece) is shown in the figure below. These labels will be attached to the retail boxes.

**Table 1: Illustration of labels for the test product for 1-piece devices. Lot number and expiry date will be added before release of products.**

#### **2.4. Clinical investigation intended use of device**

The ostomy bag is intended to collect output from a stoma. The adhesive is intended to fix the bag and adhere to intact peristomal skin around the stoma.

#### **2.5. Intended population for the device**

The intended population for the device is people with an ileostomy or a colostomy with liquid output.

#### **2.6. Handling and training**

The handling of the test products is described in details in the Instruction for Use (IFU), which is included in all boxes with test products. It is stated in the IFU that the test products are for single-use and must be stored horizontally under dry and not freezing conditions, and should be kept away from direct sunlight. Reprocessing, washing, disinfection, and sterilisation may compromise product characteristics, causing additional risk of physical harm to or infection of the user.

 Product Risk Management Report – Clinical Study CP300 Genesis (VV0227119)

All Investigators / investigator representatives will receive training by sponsor / investigator in the handling and correct use of the test products. The Investigator/investigator representative will train the subjects in the correct use of the test products.

## **2.7. Comparator product(s)**

As the comparator product is already on the market and will be used within the intended use in this clinical investigation, it is not considered an investigational device according to ISO 14155:2011 and is thus not described here. Please refer to the ISO 14155:2011 for details.

### 3. Justification for the conduct of the clinical investigation

People with abdominal stomas (especially ileostomists) have, despite development of better stoma products, problems with leakage [REDACTED] influence quality of life negatively [2]. To overcome this, Coloplast A/S has developed a new stoma product with a baseplate [REDACTED]

[REDACTED] The aim is to seek knowledge of whether the new baseplate can protect the skin [REDACTED]

## 4. Investigational device and clinical investigation risks and benefits

The clinical investigation is conducted in accordance with current law and applicable standards (see section 12). The rights, safety and well-being of the subjects shall prevail over science and society. All investigators and investigator representatives will be instructed in performing their job with conscientiousness and care.

### 4.1. Anticipated clinical benefits

The test products contain a [REDACTED]

[REDACTED] The outcome of this investigation will contribute with important information for development of products for subjects with a stoma, regarding [REDACTED]  
[REDACTED]

### 4.2. Anticipated risks and disadvantages

#### Anticipated risks

A number of risks connected to use of the test product have been identified in the Product Risk Assessment. All risks will be mitigated before release of products for the clinical investigation. The risk management process has been performed in accordance with the requirements stated in ISO 14971:2012 and in accordance with internal Coloplast procedures, including design verification, validated test methods, risk analysis and completion of a biological report for the test product.

The following risks will also be mitigated by actions during the clinical investigation, specified in this Clinical Investigation Plan:

- **Irritated skin (intact or non-intact):** Use of the product can lead to intact or non-intact irritated skin. To mitigate and reduce the risk, the users will be trained, according to the IFU, in preparation of the product (e.g. hole size), preparation of skin before application (e.g. cleaning and wiping), application of product (e.g. correct position and applying pressure to the baseplate), removal of product and storage of the product.
- **Strangulation of a stoma,** [REDACTED] was stated as the root cause to a Serious Adverse Event in a previous clinical investigation (CP264). Therefore, [REDACTED]  
[REDACTED]

#### Residual risks

Residual risks will be assessed after mitigation of the risks.

#### Disadvantages

Disadvantages during the investigation could be the extra workload related to completion of questionnaires, visits at site and using the clinical app at each change of product.

---

 Danish Ethical Committee registration number: H-17031767

Danish Competent Authorities registration number: 2017102759 and CIV-ID: CIV-17-10-02-021866

### **Interactions with concomitant medication**

There is no known interaction between the use of the stoma products used in the clinical investigation and concomitant medication.

### **4.3. Benefits versus risks**

The participating subjects will contribute with important information for development of new stoma products, that may have less negative impact on the peristomal skin. Due to the actions taken to mitigate the above-mentioned risks, the risks and disadvantages when participating in this clinical investigation are estimated as low. The subject's health will not benefit directly from this investigation but they may benefit from the use of the new stoma product through less irritated peristomal skin and improved quality of life and in the future.

## 5. Aim, objectives and hypotheses of the clinical investigation

### 5.1. Aim

The **aim** of the investigation is to investigate the performance of a baseplate with a [REDACTED]

### 5.2. Objective

The **primary objective** is to investigate whether a new baseplate [REDACTED]

The **secondary objective** is to investigate the safety [REDACTED]

### 5.3. Hypotheses

The hypothesis is that [REDACTED]. As this investigation is explorative, there is no formal criteria for success.

## 6. Design of the clinical investigation

### 6.1. General

This investigation is a controlled, comparative, multicentre investigation, that consist of two test periods. During Test Period 1 the subjects will be asked to use SenSura® Mio (Comparator) for baseline data for 14 (-2/+15) days. Hereafter the subjects will be asked to use the test product for 28 (-4/+12) days during Test Period 2. During the test periods the subjects can change their product as often as needed, but at least every third day.

Before the test periods the subjects are invited for an inclusion visit (V0). Subjects sign all consent forms at this visit before continuing the investigation. Hereafter, the subjects will complete five test visits (V1, V2, V4, V5 and V6) and one safety visit at site (V3). After termination, a follow-up visit may be conducted at the subject's home.

Biological materials (faeces) will be collected during the investigation for analysis only related to this investigation. Therefore, an Investigational BioBank will be created for this purpose. The samples of biological materials will be stored in a separately CP300 allocated freezer at site, and send on an ongoing basis to Coloplast A/S, Humlebæk, Denmark. The samples of biological materials will not be stored longer than it takes to collect and analyse the samples. The sample will be destroyed directly after analysis. The Biobank will be closed when all output samples have been analysed and destroyed, or at three months after last patient out.

Please see section 6.4.1 Clinical Investigation-related Procedure for more information about procedures during the investigation.

### 6.1.1. Endpoints

**Table 2: List of Primary, Explorative and Safety Endpoints.** Investigator can delegate the task to trained site personnel. Only completed by subject at the first 14 change of products during test period 1 and completed by subject at every change of product during test period 2.

	Endpoint	Type of assessment	Assessed by	V1	V2	V3	V4	V5	V6	Product change
	[REDACTED]	[REDACTED]	[REDACTED]	[REDACTED]	[REDACTED]	[REDACTED]	[REDACTED]	[REDACTED]	[REDACTED]	
	[REDACTED]	[REDACTED]	[REDACTED]	[REDACTED]	[REDACTED]	[REDACTED]	[REDACTED]	[REDACTED]	[REDACTED]	
	[REDACTED]	[REDACTED]	[REDACTED]	[REDACTED]	[REDACTED]	[REDACTED]	[REDACTED]	[REDACTED]	[REDACTED]	
	[REDACTED]	[REDACTED]	[REDACTED]	[REDACTED]	[REDACTED]	[REDACTED]	[REDACTED]	[REDACTED]	[REDACTED]	
	[REDACTED]	[REDACTED]	[REDACTED]	[REDACTED]	[REDACTED]	[REDACTED]	[REDACTED]	[REDACTED]	[REDACTED]	
	[REDACTED]	[REDACTED]	[REDACTED]	[REDACTED]	[REDACTED]	[REDACTED]	[REDACTED]	[REDACTED]	[REDACTED]	
	[REDACTED]	[REDACTED]	[REDACTED]	[REDACTED]	[REDACTED]	[REDACTED]	[REDACTED]	[REDACTED]	[REDACTED]	
	[REDACTED]	[REDACTED]	[REDACTED]	[REDACTED]	[REDACTED]	[REDACTED]	[REDACTED]	[REDACTED]	[REDACTED]	
	[REDACTED]	[REDACTED]	[REDACTED]	[REDACTED]	[REDACTED]	[REDACTED]	[REDACTED]	[REDACTED]	[REDACTED]	

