#### 6.1.4. Rationale for selection and measurement of endpoints

The primary endpoint, TEWL, is a standardised non-invasive method for describing the barrier function of the skin. Damage to the skin surface will lower the barrier of the skin and thereby increase the water loss. This measurement is therefore used as primary endpoint

Additional skin measurements, assessments and the skin condition endpoints are all parameters describing the skin. Therefore, these are also essential to investigate if the new baseplate

The median wear time per subject in each period is used as endpoint, as it is considered a robust estimation of wear time.

Adverse events, device deficiencies, concomitant medication and safety questions comprise safety parameters. Qualitative interviews will give a subjective insight in the subject experience with the test product.

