#### 6.1.5. Discussion of clinical investigation design

The new test product is intended for people with an ileostomy and for colostomists with liquid output. The two groups experience the same issues regarding leakage and skin problems and could therefore benefit from the product.

SenSura® Mio and SenSura® users are chosen and will be considered as one group, since results from a previous investigation showed no difference between the two user groups regarding inner circle TEWL (primary endpoint).

The duration of Test Period 1 (14 (-2/+15) days) and two test visits in the period is found adequate to assess baseline data on the wear time, leakage pattern and skin condition of the subject. The test product is tested for 28 (-4/+12) days to ensure that the skin will have time to adjust to the new conditions, reach a steady state, and for the subjects to test an adequate number of products to give a thorough evaluation of the products.

To follow safety closely and ensure proper compliance and no unexpected events related to the test product, the first five subjects will be enrolled at the Coloplast Humlebæk Site DK001 (Sponsor). In addition, and due to Christmas holiday, follow-up logistics and planning purpose, the following subjects, at other sites than DK001, will be invited for the test visit 1 during week 49-51 (December 2018) and for their test visit 2 during week 1 and 2 (January 2019).

 CP275 – A clinical investigation evaluating three new 1-piece ostomy products

Danish Ethical Committee registration number H-17005054/Danish Competent Authorities registration number DMA-2017022387

In this investigation, a part of the information about the products is obtained via interviews (qualitative data). The interviews allow for detailed questions (in the form why, when, how) that can be adjusted individually per each subject's experience. This gives more details about the subject's experience with the test product. However, some drawbacks also occur with this method of obtaining information, as the interview data is subjective and cannot be quantified. The interviews may also cause a positive bias towards Coloplast. Thus, in this explorative investigation, the main endpoints are obtained by CRFs (from all subjects) and the interviews are used for supplementary information. The data collected by interviews will be handled confidentially, as all other data collected in this investigation.

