## 6.2. Investigational device and comparator(s)

Subjects using 1-piece open products are expected to change their products every day. Therefore, they are expected to use 14 (-2/+15) of the comparator products during Test Period 1 and 28 (-4/+12) of the test products during Test Period 2.

To take the variety of visit windows, change patterns and distribution logistics to sites in different countries into account, a safety margin of products has been added. Therefore, the total number of products for this investigation is 2000 1-piece products.

The test product is based on the SenSura® Mio 1-piece products already on the market. Therefore, the comparator in this investigation is:

- 1-piece
  - SenSura® Mio 1-piece open, flat, maxi, neutral grey, 10-55 mm and circle filter

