#### Analysis of the exploratory endpoint

[REDACTED]

To include the information from the reference spot on the abdominal site, all the above described analyses will be performed as explorative analyses with the dependent variable as the difference between the endpoint and the mean of the corresponding measurements from the reference spot.

[REDACTED]

From this model the difference in leakage area and distance between products will be estimated

As this is the first time the “skin condition endpoints (Assessed at every product change)” have been included in a study, the data will be used to evaluate how the results can be summarised, interpreted and analysed in upcoming studies.

As it is an exploratory study no adjustment for multiple testing will be applied.

Photos will be evaluated visually in this exploratory study. Collected baseplates and output samples will not be evaluated statistically.

All other endpoints will be listed or summarized by descriptive statistics. Additional summaries can be made for endpoint only collected in the steady state periods.

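### Items under Table 2 note 2 stop after 14 comparator changes but continue throughout the test product, so a long Test Period 1 loses its latest comparator records

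*Combined protocol and SAP*

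**What the plan says.** **Recording rule.** Section 6.1.1, Table 2, note 2 treats the two periods differently: "Only completed by subject at the first 14 change of products during test period 1 and completed by subject at every change of product", the second half referring to Test Period 2. The rows of Table 2 are redacted, so the items that carry the note cannot be named. Section 6.4.1, under Product change, sets no limit in either period. There the subject records skin condition, accessory use, pain or discomfort and the reason for changing each time a product is changed.

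**Length of the periods.** Section 6.1 plans "SenSura® Mio (Comparator) for baseline data for 14 (-2/+15) days", after which "the subjects will be asked to use the test product for 28 (-4/+12) days during Test Period 2". Section 6.2 adds: "Subjects using 1-piece open products are expected to change their products every day". It continues: "Therefore, they are expected to use 14 (-2/+15) of the comparator products during Test Period 1 and 28 (-4/+12) of the test products" in Test Period 2. Section 6.3.3 gives a range of 12 to 39 days for Test Period 1. It also schedules sites other than DK001 for Visit 1 in weeks 49 to 51 of 2018 and Visit 2 in weeks 1 and 2 of 2019.

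**Analysis.** Section 6.1.4 states: "The median wear time per subject in each period is used as endpoint". In Section 7.1 the per-change skin items serve to learn how such data might be handled in later studies. A product difference in leakage area and distance comes from a model whose description is redacted, and endpoints without a model are listed or described. The section adds: "Additional summaries can be made for endpoint only collected in the steady state periods". It defines no window for this. No readable text says how unequal numbers of recorded changes are to be handled.

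**The concern.** The two recording rules cannot both be followed in Test Period 1 for the same item, and what is not recorded at a change cannot be recovered later.

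The limit also does not thin the comparator data at random. It always removes the latest changes, and only on the comparator. The test product is recorded to the end of a period planned at 28 days, a length chosen in Section 6.1.5 partly "to ensure that the skin will have time to adjust to the new conditions, reach a steady state". So the plan itself expects responses on the test product to move with time. If the comparator record stops at change 14, the two products may be described over different stretches of use, and the comparator data that could show whether this matters are missing. The simpler loss is precision: fewer comparator records per subject than the period could supply.

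**Working it through.** **1. The plan's own figures.** Days × 1 change per day gives 14 comparator changes (12 to 29) and 28 test-product changes (24 to 40), exactly as in Section 6.2. At the nominal 14 days the limit keeps 14/14 = 100% of comparator changes.

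**2. Length of Test Period 1 under the Christmas schedule.** The comparator is handed out at Visit 1 and the test product at Visit 2 (Section 6.4.4), so the visit gap is the period length. Taking calendar weeks, Monday to Friday, Visit 1 falls on 3 to 21 December 2018 and Visit 2 on 31 December 2018 to 11 January 2019.
- Shortest gap: 21 to 31 December, 10 days.
- Longest gap: 3 December to 11 January, 39 days.
- Mid-window: Wednesday of week 50 to Wednesday of week 1 is 21 days; to Wednesday of week 2 it is 28 days.

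Section 6.1.5 places the first five subjects at DK001, Section 6.3.3 the first ten. If DK001 enrols no more than that, 15 to 20 of the 25 subjects follow this schedule.

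**3. Share of comparator changes lost.** Loss = 1 − 14/(days × changes per day), or zero if that is negative.

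| Test Period 1 | one change every 3 days | 1 per day | 2 per day |
|---|---|---|---|
| 14 days | 0% | 0% | 50% |
| 21 days | 0% | 33% | 67% |
| 28 days | 0% | 50% | 75% |
| 29 days | 0% | 52% | 76% |
| 39 days | 0% | 64% | 82% |

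**4. Precision.** If changes within a subject are independent with equal variance (an assumption), the within-subject part of the standard error of a comparator mean grows by √(21/14) = 1.22 at 21 days and √(28/14) = 1.41 at 28 days. The between-subject part does not change.

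**5. Possible bias, for two identical products.** The documents give no time curve, so every pattern here is assumed. In (a) and (c) an initial excess decays as exp(−t/τ), with t counted in daily changes, τ = 3, 7 or 14, and 28 test-product changes. Results are test minus comparator, as a share of the initial excess.
- **(a) Settling restarts with each product.** With the limit: −0.12, −0.20, −0.21. Without it: unchanged at 14 days; −0.04, −0.08, −0.09 at 21 days; 0.00, +0.01, +0.01 at 29 days.
- **(b) Only the test product needs settling.** Let k be the late rate divided by the early rate, with the comparator already at the late rate. The test/comparator ratio is (1 + k)/(2k). At k = 0.7 this is 1.7/1.4 = 1.21, with or without the limit. Using only the first 14 changes on each product gives 1/k = 1.43.
- **(c) One trend runs across both periods.** At 29 days with the limit: −0.25, −0.46, −0.60. Without it: −0.12, −0.25, −0.38. Using the first 14 changes on each product leaves −0.25 to −0.57 across periods of 14 and 29 days.
- **(d) No trend.** Zero under any rule.

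If the excess is unfavourable, (a) and (c) favour the test product and (b) goes against it.

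**The case against.** A reader might infer that note 2 tilts the per-change comparison towards the test product, so that identical products would look different. The documents do not support that.

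- Entrants must already use a flat SenSura Mio or SenSura (Section 6.3.1), so many are habitual users of the comparator or a close relative.
- The sentence in Section 6.1.5 about adjusting concerns the test product. The one before it calls Test Period 1 adequate for baseline wear time, leakage and skin condition.
- Pattern (b) is therefore at least as plausible as (a), and its sign is opposite.
- At 14 days with daily changes the imbalance of 14 against 28 comes from the period lengths, not from the note.
- The marked rows and part of Section 7.1 are redacted, the readable plans for most diary items are descriptive, and there are no success criteria (Section 7.5). The steady-state summary is optional, and nothing shows that a familiar comparator lacks a steady state.

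All of this stands against a claimed direction or size. It also tells against replacing the comparison with the first 14 changes on each product. That would discard the settled test-product data and, under (b) at k = 0.7, move the ratio from 1.21 to 1.43.

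It does not dispose of the recording problem. SenSura users do switch to Mio, and subjects are asked to give up adhesive remover and rings or seals (Section 6.4.3), so a time trend on the comparator cannot be excluded. The note might apply only to an item hidden by redaction, but each subject-completed item readable under Product change in Section 6.4.1 is required at each change.

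**Conclusion.** The point holds as a recording inconsistency with an avoidable loss of comparator data. Note 2 and Section 6.4.1 disagree. Under the plan's own scheduling at sites other than DK001, a daily changer loses about 33% to 50% of comparator records at mid-window and 52% at 29 days, always from the end of the period. These shares rest on one change per day (Section 6.2) and mid-window visits. With changes every third day nothing is lost, and with two a day half is lost even at 14 days.

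The consequence is lower comparator precision and, if responses vary with time on product, a comparison over unequal stretches of use. The documents do not establish the direction or size of any resulting bias; the figures in step 5 are illustrations under assumed curves. The primary endpoint, TEWL measured at visits, is unaffected.

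**What to change.** 1. Delete the 14-change limit from Table 2 note 2, so that it agrees with Section 6.4.1 and the items are recorded at each change in both periods.
2. In Section 7.1, summarise product-change endpoints by change number or day within each period, so that any time trend is visible on both products.
3. Keep the all-data comparison. Show an equal-change-number comparison beside it as a sensitivity summary only, not as a replacement.
4. Reconcile the two ranges for Test Period 1 (Sections 6.1 and 6.3.3), since the amount of comparator data depends on them.

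The cost is some extra diary entries for subjects with a long Test Period 1: for a daily changer, 21 − 14 = 7 to 28 − 14 = 14 more at mid-window. Under pattern (a), removing the limit cuts the illustrative bias from 0.12–0.21 to 0.04–0.09 of the initial excess at 21 days and to about zero at 29 days. It adds none under pattern (b). It changes nothing at 14 days with daily changes. Neither recording every change nor the equal-number summary removes a trend that runs across both periods, because the product order is fixed; the report should say so.
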